6.7.2 Key Secondary Analysis

The key secondary efficacy endpoint is the change from study baseline (Screening Visit) to Visit Week 52 in the Adaptive Behavior Composite (ABC) score as measured by the VABS-II. The key secondary analysis will compare the treatment groups using a linear mixed model repeated measures (MMRM) analysis. The repeated measures are the change from baseline ABC scores obtained at the scheduled Visit Weeks 16, 28, 40, and 52, respectively. The model will include fixed categorical effects for treatment, visit week, treatment by visit week interaction, baseline GCA classification factor (either ≤ 70 or >70), baseline age group (either <6 years or ≥ 6 years),

treatment by baseline GCA classification factor interaction, treatment by baseline age group interaction, interaction between baseline GCA classification factor and baseline age group, genotype, and the baseline ABC score as a continuous covariate.

SAS Proc Mixed with restricted maximum likelihood estimation (REML) and an unstructured within-patient covariance structure will be used. If this model fails to converge, a first order autoregressive (AR(1)) covariance structure will be used instead. The Kenward-Roger approximation will be used to estimate denominator degrees of freedom for tests of fixed effects. The assumptions of the model, including normality, will be evaluated using residual and other diagnostic plots of model fit.

From this model, least squares means, standard errors, treatment differences in least squares means, and 95% confidence intervals will be estimated for each time point. The significance test will be based on the treatment comparison of least squares means at Visit Week 52 from this model, and a p-value will be presented for this time point only. Estimated least squares means for change from baseline and the observed absolute values (\pm SE) by treatment group will be plotted over time.

The sample SAS code is presented in [appendix 9.2.2](#).

6.7.3 Other Secondary Analyses

The following secondary efficacy endpoints will be analyzed using a MMRM analysis in the same manner as described above for the key secondary endpoint with the continuous covariate corresponding to the baseline score for each measure:

- The change from baseline to Visit Weeks 16, 28, 40, and 52 in standard scores in cluster areas of the DAS-II: Verbal, Nonverbal, Spatial, and Special Nonverbal Composite (SNC)
- The change from baseline to Visit Weeks 16, 28, 40, and 52 in the standard scores of the VABS-II: Communication, Daily Living Skills, Socialization, and Motor Skills
- The change from baseline to Visit Weeks 16, 28, 40, and 52 in the T scores for the six core subtests of the DAS-II/Early Years: Verbal Comprehension, Picture Similarities, Naming Vocabulary, Pattern Construction, Matrices and Copying

Due to small sample size of ITT subjects who have been evaluated by the DAS-II Test for school age, the six core subtests for the DAS-II/School Age, including Recall of Designs, Word Definitions, Pattern Construction, Matrices, Verbal Similarities and Sequential and Quantitative Reasoning, cannot be analyzed using the MMRM model.

The estimated least squares means and 95% confidence intervals on the treatment comparison at Visit Weeks 16, 28, 40 and 52 from MMRM model will be presented in Forest plots for GCA score, standard scores for SNC and each of the three clusters (Verbal, Nonverbal, Spatial), and T scores for each of the six above-mentioned core subtests of the DAS-II/Early Years.

All other secondary efficacy endpoints listed above will be summarized descriptively by treatment group over time. When there is $>$ or \geq or $<$ or \leq recorded in the data, the inequality sign will be ignored for the age equivalents summary and the DQ calculation. DQ is defined as Age equivalent provided by the test $\times 100$ /Chronological age.

Mean observed values by treatment group will be plotted over time. This includes the following endpoints:

- The change from baseline to Visit Weeks 16, 28, 40, and 52 in the T scores, age equivalents and DQ for the core subtests of the DAS-II: Verbal Comprehension, Picture Similarities, Naming Vocabulary, Pattern Construction, Matrices and Copying for the DAS-II/Early Years; and Recall of Designs, Word Definitions, Pattern Construction, Matrices, Verbal Similarities and Sequential and Quantitative Reasoning for the DAS-II/School Years
- The change from baseline to Visit Weeks 16, 28, 40, and 52 in the v-scale scores, age equivalents and DQ for the sub-domains of the VABS-II: Communication (Receptive, Expressive, Written), Daily Living Skills (Personal, Domestic, Community), Socialization (Interpersonal Relationships, Play and Leisure Time, Coping Skills), Motor Skills (Gross, Fine)
- Change from baseline to Visit Weeks 16, 28, 40, and 52 in v-scale scores and the observed maladaptive levels of the VABS-II Maladaptive Behavior Index and its sub-scales (Internalizing, Externalizing).

By-patient listings will be presented for the following parameters:

- Standard scores and percentiles in patients evaluated by the DAS-II test (either version) for each cluster
 - Verbal
 - Nonverbal
 - Spatial
 - GCA
 - SNC
- T scores, percentiles of T scores, age equivalents, chronological age and DQ for patients evaluated by the DAS-II test for Early Years for each core subtest
 - Verbal Comprehension (Vcom)
 - Picture Similarities (Psim)
 - Naming Vocabulary (Nvoc)
 - Pattern Construction (Pcon)
 - Matrices (Mat)
 - Copying (Copy)
- T scores, percentiles of T scores, age equivalents, chronological age and DQ for patients evaluated by the DAS-II test for School Age for each core subtest
 - Recall of Designs (RDes)

- Word Definitions (WDef)
- Pattern Construction (Pcon)
- Matrices (Mat)
- Verbal Similarities (VSim)
- Sequential & Quantitative Reasoning (SQR)

- Standard scores and percentile in patients evaluated by the VABS-II test for ABC and each domain
 - Communication
 - Daily Living Skills
 - Socialization
 - Motor Skills

- v-scale scores, age equivalents, chronological age and DQ for patients evaluated by the VABS-II test for each sub-domain
 - Communication (Receptive, Expressive, Written),
 - Daily Living Skills (Personal, Domestic, Community),
 - Socialization (Interpersonal Relationships, Play and Leisure Time, Coping Skills),
 - Motor Skills (Gross, Fine)

- v-scale scores and Maladaptive levels of Maladaptive Behavior Index and its sub-scales (Internalizing, Externalizing) in VABS-II

A listing for the substudy population will be presented by patient and visit for the following parameters:

- Raw score, age equivalents versus chronological age, as well as DQ, composite score and percentile for each patient evaluated by the BSID-III test and each domain
 - Motor (Fine, Gross)
 - Language (Receptive, Expressive)
 - Cognitive

6.7.4 Subgroup Analyses

Subgroup analyses will be performed for the following subgroups:

- Baseline GCA classification groups. For this analysis, patients with a baseline GCA score of > 70 will be classified as having “Moderate” cognitive impairment, while patients with a baseline GCA score ≤ 70 will be classified as having “Severe” cognitive impairment. The randomization is stratified by this classification variable to ensure treatment group balance within these subgroups
- Baseline age group (either < 6 years or ≥ 6 years)
- Exploratory analysis for baseline age group (either < 55 months or ≥ 55 months).

Subgroup analyses are planned for the change from baseline in GCA and ABC standard scores, respectively. An MMRM model will be used to test for treatment by subgroup interactions. Interactions with a significance level of less than 10% will be considered potentially important and flagged for further clinical assessment. In general, the model will include fixed categorical effects for treatment, visit week, treatment by visit week interaction, subgroup, treatment by subgroup interaction, subgroup by visit interaction and the 3-way interaction between treatment, visit week and subgroup, and genotype. The p-values of interaction terms will be presented, as well as the least squares means and its 95% confidence intervals by treatment and visit for each subgroup classification factor. Descriptive statistics of the observed and change from baseline GCA and ABC standard scores will also be presented by treatment and visit week within each subgroup.

Additionally, the subgroup analysis will be performed for the age subgroup with baseline age < 6 years which may be the patient population with the most potential to benefit from the idursulfase-IT treatment. The change from baseline GCA score obtained at Visit Week 52 will be compared between the treatment groups using MMRM analysis. The repeated measures are the change from baseline GCA score obtained at the scheduled Visit Weeks 16, 28, 40, and 52, respectively. The model will include fixed categorical effects for treatment, visit week, treatment by visit week interaction, baseline GCA classification factor (either ≤ 70 or > 70), treatment by baseline GCA classification factor interaction, genotype and the baseline GCA score as a continuous covariate. Due to small sample size of ITT subjects with baseline age ≥ 6 years, MMRM model will not be applied for this age subgroup.

The sample SAS code is presented in [appendix 9.2.9](#).

As exploratory analysis, the subgroup analysis will also be performed for the age subgroup with baseline age < 55 months and ≥ 55 months using an MMRM analysis in the same manner as described above for age subgroup with baseline age < 6 years.

The subgroup analyses will also be performed for the baseline GCA subgroup with baseline GCA score ≤ 70 and baseline GCA score > 70 . The change from baseline GCA score obtained at Visit Week 52 will be compared between the treatment groups using MMRM analysis. The repeated measures are the change from baseline GCA score obtained at the scheduled Visit Weeks 16, 28, 40, and 52, respectively. The model will include fixed categorical effects for treatment, visit week, treatment by visit week interaction, baseline age group (either <6 years or ≥ 6 years), treatment by baseline age group interaction, genotype and the baseline GCA score as a continuous covariate.

The sample SAS code is presented in [appendix 9.2.10](#).

The estimated least squares means and 95% confidence intervals on the treatment comparison at Visit Weeks 16, 28, 40, and 52 from MMRM model will be presented in Forest plots, including subgroup of baseline age < 6 years, baseline age < 55 months and baseline age ≥ 55 months, baseline GCA score ≤ 70 and baseline GCA score > 70 .

As exploratory analyses, the primary and key secondary MMRM models will be refit including the continuous baseline covariate by treatment interaction term and the 3-way interaction among treatment, visit week and the continuous baseline covariate in the model. The p value for the interaction terms and the estimated least squares means with their standard errors and 95% confidence intervals by treatment and visit at quartiles of GCA at baseline (25th, 50th and 75th percentiles) will be presented.

Due to small sample size of ITT Population with baseline age ≥ 6 years, MMRM model may fail to converge when low count of subjects with baseline age ≥ 6 years exists in either treatment group. If this model fails to converge, the treatment by baseline age group interaction will be removed from the model.

The sample SAS code is presented in [appendix 9.2.11](#).

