10.5.4 Exploratory Analyses

As exploratory analyses, the primary and key secondary MMRM models will be refit including the continuous baseline covariate by treatment interaction term in the model. Estimated least square means and 95% CIs for each treatment adjusting at the 25th, 50th, and 75th percentiles of the pooled baseline covariate distribution will be evaluated.

Additional subgroup analyses are planned for exploratory purposes for the change from baseline in GCA and ABC scores. An MMRM model will be used to test for subgroup interactions at the 10% significance level. In general, the model will include effects for treatment, visit week, treatment by visit week interaction, subgroup, treatment by subgroup interaction, subgroup by visit interaction and the 3-way interaction between treatment, visit and subgroup. The p-values from interaction tests will be presented, as well as the least square means and 95% CIs by treatment and visit within each subgroup. Descriptive statistics of observed values and change from baseline will also be presented by treatment and visit week within each subgroup.

A subgroup analysis will be performed for baseline GCA groups. For this analysis, patients with a baseline GCA score of greater than 70 will be classified as having “Moderate” cognitive impairment, while patients with a baseline GCA score equal to or below 70 will be classified as having “Severe” cognitive impairment. The randomization is stratified by this classification variable to ensure treatment group balance within these subgroups. Similar exploratory subgroup analyses may be performed for age group (either ≤ 6 years or > 6 years), language, geographic region or other baseline factors using MMRM.

A linear random coefficients model (ie, random slope and intercept for continuous time) will be fit for the primary and key secondary endpoints if appropriate. The average of the subject-specific slope estimates from the model will be compared between treatment groups using the two-sample t-test. To explore the relationship between composite scores and their components, correlations between the GCA and ABC scores (absolute value and change from baseline) and their respective domain scores will be estimated. Scatter plots will also be presented.

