8. STATISTICAL/ANALYTIC ISSUES

8.1 Adjustment for Covariates

Analyses of the change from baseline in efficacy endpoints utilizing MMRM methodology will adjust for the baseline score of the parameter of interest as a continuous covariate in the model. As the randomization of the study is stratified by the baseline GCA classification factor (either ≤ 70 or > 70), MMRM analyses will also take into account the GCA strata as a classification factor. The baseline age group (either < 6 years or ≥ 6 years) is also a categorical covariate in the MMRM analysis.

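### The treatment-by-subgroup interaction MMRM in SAP 6.7.4 is listed without the baseline score, GCA class and age group that SAP 8.1 requires

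*SAP*

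**What the plan says.** SAP 6.7.4 names three subgroup factors: GCA class (<=70, >70), age below or from 6 years, and, as exploratory, age below or from 55 months. It covers both endpoints: "Subgroup analyses are planned for the change from baseline in GCA and ABC standard scores, respectively". The interaction model has treatment, visit week, treatment by visit, subgroup, treatment by subgroup, and then "subgroup by visit interaction and the 3-way interaction between treatment, visit week and subgroup, and genotype". The consequence of the test is stated: "Interactions with a significance level of less than 10% will be considered potentially important and flagged for further clinical assessment".

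SAP 8.1 sets a general rule for MMRM analyses of change. They "will adjust for the baseline score of the parameter of interest as a continuous covariate in the model"; "MMRM analyses will also take into account the GCA strata as a classification factor"; and age group (<6, >=6 years) "is also a categorical covariate in the MMRM analysis".

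Protocol 10.5.4 has the same list without genotype: "In general, the model will include effects for treatment, visit week, treatment by visit week interaction, subgroup, treatment by subgroup interaction", followed by subgroup by visit and the three-way term. Protocol 10.8.2 requires the baseline score and the GCA stratum, but not age group.

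The other models in SAP 6.7.4 name their covariates. The within-subgroup GCA models for age <6 years and for the two 55-month groups include GCA class and continuous baseline GCA. Those for GCA <=70 and >70 include age group and continuous baseline GCA.

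**The concern.** An analyst who programs the listed terms will fit an interaction model that departs from SAP 8.1. Three outputs are exposed:

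- the interaction p-values behind the 10% flag;
- the least squares means by treatment, visit and subgroup from that model. For age >=6 years, 6.7.4 rules out a separate MMRM, so these would be the only model-based means planned for that group;
- the ABC results by categorical subgroup. The within-subgroup models are specified for GCA only, so for ABC the interaction model is the only one, and baseline ABC is not in it.

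For GCA, the interaction p-value and the forest-plot estimates would come from differently adjusted models. They could disagree for reasons that have nothing to do with effect modification. SAP 4.2 expects baseline GCA to be a key prognostic factor, so it is an odd term to leave out when genotype, with five categories in SAP 6.5, is in. Randomization is stratified by GCA class and not by age, so nothing in the design balances GCA class within age groups.

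**Working it through.** **Terms side by side**

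| SAP 6.7.4 model | Endpoint's baseline score | GCA class | Age group (<6, >=6) |
|---|---|---|---|
| Interaction, subgroup = GCA class | not listed | is the subgroup | not listed |
| Interaction, subgroup = <6 / >=6 years | not listed | not listed | is the subgroup |
| Interaction, subgroup = <55 / >=55 months | not listed | not listed | not listed |
| Within age <6, <55 or >=55 months (GCA only) | listed | listed | not listed |
| Within GCA <=70 or >70 (GCA only) | listed | defines the group | listed |
| Required by SAP 8.1 | yes | yes | yes |

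The code in SAP 9.2.11 contains baseline GCA, GCA class and age group. It belongs to the refit with continuous baseline by treatment, not to the categorical-subgroup model, for which no code is given.

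**The plan's own figure.** SAP 4.2 gives 48 patients (32 and 16), SD of change 11.6, difference 11, two-sided 5%, 10% missing, power 80%. With 28.8 and 14.4 evaluable, SE = 11.6 x sqrt(1/28.8 + 1/14.4) = 3.74. The noncentral t gives 81.8%; with 28 and 14 it gives 80.7%. The figure reproduces and is not in dispute. The plan states no figure for the interaction model.

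**Effect on the interaction standard error.** I use a single-visit (Week 52) approximation:

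SE = SD x sqrt(1-r^2) x sqrt(sum over both subgroups of 1/n_IT + 1/n_control)

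Here r is the correlation of baseline score with change, given the terms already in the model. Neither r nor the subgroup split is in the documents, so both are assumptions. With r=0 and SD 11.6:

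- 50/50 split: 11.6 x sqrt(2 x (1/14.4 + 1/7.2)) = 7.49
- 20/80 split: 11.6 x sqrt(1/5.76 + 1/2.88 + 1/23.04 + 1/11.52) = 9.36

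Power for an 11-point interaction at the 10% level is approximately Phi(11/SE - 1.645).

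| r | sqrt(1-r^2) | SE, 50/50 | Power | SE, 20/80 | Power |
|---|---|---|---|---|---|
| 0 (as listed) | 1.00 | 7.49 | 43% | 9.36 | 32% |
| 0.2 | 0.98 | 7.34 | 44% | 9.17 | 33% |
| 0.3 | 0.95 | 7.14 | 46% | 8.93 | 34% |
| 0.5 | 0.87 | 6.48 | 52% | 8.11 | 39% |

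For ABC (SD 10.5 in SAP 4.2) the unadjusted SEs scale by 10.5/11.6, to 6.78 and 8.47. The ratios are the same.

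**GCA in the GCA-class model.** SAP 9.3.2 simulates baseline GCA as normal with mean 70 and SD 15, restricted to 55-85. Under that distribution the class explains about 73% of baseline GCA variance. If class acts on change only through baseline, the further gain from the continuous score is sqrt((1-r^2)/(1-0.73r^2)). That is sqrt(0.91/0.934) = 0.99 at r=0.3 and sqrt(0.75/0.8175) = 0.96 at r=0.5, so little is lost there. The same does not follow for ABC, because GCA class is only an indirect proxy for baseline ABC.

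**The case against.** The best reply is that there is no conflict. SAP 8.1 is a general rule. The list in 6.7.4 is introduced as holding in general and as a list of fixed categorical effects, so a continuous covariate need not appear in it. On that reading 8.1 supplies baseline GCA or ABC. This reading is open, so the documents do not show that an unadjusted model will be run. It has two weaknesses. GCA class and age group are categorical, and they are missing too. The other MMRM descriptions in SAP 6.7 name the baseline covariate or refer to a model that does.

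A second reply is that the main GCA subgroup estimates are already adjusted. This is true of the forest plots. It does not cover the interaction p-values, the interaction model's own means, or ABC.

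A third is that the SAP's simulation found almost no change from adding the stratum (9.3.2), and nearly equal observed and model standard errors at Month 13, 3.377 and 3.382 (9.3.4.1). This is not evidence against adjustment. The change data described there have means and covariances that do not depend on baseline, so no gain could appear.

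The limit on consequence stands in full. Protocol 10.5.4 calls these analyses exploratory, and SAP 8.5 treats everything outside the three gatekept families as supportive.

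**Conclusion.** The specification is inconsistent and should be settled before the analysis. As listed, the interaction model omits covariates that SAP 8.1 requires and that the neighbouring models carry. The cost is a less precise interaction test and less precise means than the collected data allow, and a mismatch with the adjusted within-subgroup GCA estimates.

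The size is modest and rests on assumed values of r and of the subgroup split. Adjustment reduces the interaction SE by about 2% at r=0.2, 5% at r=0.3 and 13% at r=0.5. For GCA in the GCA-class model the reduction is about 1% at r=0.3 and 4% at r=0.5. The SEs are single-visit approximations; the model's interaction tests span all visits.

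Three stronger inferences are not supported:

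- A reader might infer that the primary or key secondary result is affected. Those models are specified separately, with all three covariates.
- A reader might infer that chance baseline imbalance in a small age group adds a spurious interaction on top of the quoted SE. That variation is already inside the unadjusted SE.
- A reader might infer that adjustment would rescue the test. Power for an 11-point interaction stays between 32% and 52% across the tabulated cases, with or without it.

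**What to change.** In SAP 6.7.4, amend the interaction MMRM as follows:

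- add the continuous baseline score of the endpoint being analysed (GCA or ABC);
- add GCA class (<=70, >70) when the subgroup is either age split;
- add age group (<6, >=6 years) when it is not itself the subgroup and is estimable, that is, for the GCA-class and 55-month models;
- supply sample code for the categorical-subgroup interaction model, for both endpoints.

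If the sponsor prefers the shorter model, SAP 8.1 should say that this analysis is exempt and why. The cost is one to three model terms and a block of code. All the data are already collected, and no sample size, visit or multiplicity provision changes.

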6.7.1 Primary Analysis

For the pivotal study, the primary efficacy endpoint is the change from study baseline (Screening Visit) to Visit Week 52 in the General Conceptual Ability (GCA) score as measured by the DAS-II. The primary analysis will compare the treatment groups using a linear mixed model repeated measures (MMRM) analysis (Malinckrodt et al. 2008; Siddiqui et al. 2009). The repeated measures are the change from baseline GCA score obtained at the scheduled Visit Weeks 16, 28, 40, and 52, respectively. The model will include fixed categorical effects for treatment, visit week, treatment by visit week interaction, baseline GCA classification factor (either ≤ 70 or > 70), baseline age group (either < 6 years or ≥ 6 years), treatment by baseline GCA classification factor interaction, treatment by baseline age group interaction, interaction between baseline GCA classification factor and baseline age group, genotype, and the baseline GCA score as a continuous covariate. Visit week is defined as nominal visits, unless specified otherwise.

SAS Proc Mixed with restricted maximum likelihood estimation (REML) and an unstructured within-patient covariance structure will be used. If this model fails to converge, a first order autoregressive (AR(1)) covariance structure will be used for the primary analysis. Due to small sample size of ITT Population with baseline age ≥ 6 years, MMRM model may fail to converge when low count of subjects with baseline age ≥ 6 years exists in either treatment group. If this model fails to converge, the treatment by baseline age group interaction and /or interaction between baseline GCA classification factor and baseline age group will be removed from the model. The Kenward-Roger approximation will be used to estimate denominator degrees of freedom for tests of fixed effects. The assumptions of the model, including normality, will be evaluated using residual and other diagnostic plots of model fit.

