9.2.1 Sample SAS code for the primary analysis

```
ods output estimates=est Tests3=FixF;
ods graphics on;
proc mixed data=adef data=adef covtest;
  class Trt VisitWk GCAclass Agegroup Genotype usubjid;
  model GCAchgBL = GCAclass Trt VisitWk Trt*Visitwk GCABL Agegroup Trt*GCAclass
  Trt*Agegroup GCAclass* Agegroup Genotype / ddfm=KR residual;
  repeated VisitWk / type=un subject=usubjid rcorr;
  estimate "Trt diff at Week 16" Trt 1 -1 Trt*VisitWk 1 0 0 0 -1 0 0 0 / cl;
  estimate "Trt diff at Week 28" Trt 1 -1 Trt*VisitWk 0 1 0 0 0 -1 0 0 / cl;
  estimate "Trt diff at Week 40" Trt 1 -1 Trt*VisitWk 0 0 1 0 0 0 -1 0 / cl;
  estimate "Trt diff at Week 52" Trt 1 -1 Trt*VisitWk 0 0 0 1 0 0 0 -1 / cl;
  lsmeans Trt*VisitWk / cl;
run;
```

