9.2.11 Sample SAS code for subgroup analysis testing treatment interaction

```
ods output estimates=est Tests3=FixF;  
ods graphics on;  
proc mixed data=adefc covtest;  
  class Trt VisitWk GCAclass Agegroup Genotype usubjid;  
  model GCAchgBL = Trt VisitWk GCABL Trt*Visitwk Trt* GCABL Trt*Visitwk*GCABL  
  GCAclass Agegroup Genotype/ ddfm=kr solution;  
  repeated VisitWk / type=un subject=usubjid rcorr;  
  estimate "Trt diff at Week 16" GCABL 25th_of_BL_GCA_distribution Trt 1 -1 Trt*VisitWk  
  1 0 0 0 -1 0 0 0 / cl;  
  estimate "Trt diff at Week 28" GCABL 25th_of_BL_GCA_distribution Trt 1 -1 Trt*VisitWk  
  0 1 0 0 0 -1 0 0 / cl;  
  estimate "Trt diff at Week 40" GCABL 25th_of_BL_GCA_distribution Trt 1 -1 Trt*VisitWk  
  0 0 1 0 0 0 -1 0 / cl;  
  estimate "Trt diff at Week 52" GCABL 25th_of_BL_GCA_distribution Trt 1 -1 Trt*VisitWk  
  0 0 0 1 0 0 0 -1 / cl;  
  estimate "Trt diff at Week 16" GCABL 50th_of_BL_GCA_distribution Trt 1 -1 Trt*VisitWk  
  1 0 0 0 -1 0 0 0 / cl;  
  estimate "Trt diff at Week 28" GCABL 50th_of_BL_GCA_distribution Trt 1 -1 Trt*VisitWk  
  0 1 0 0 0 -1 0 0 / cl;  
  estimate "Trt diff at Week 40" GCABL 50th_of_BL_GCA_distribution Trt 1 -1 Trt*VisitWk  
  0 0 1 0 0 0 -1 0 / cl;  
  estimate "Trt diff at Week 52" GCABL 50th_of_BL_GCA_distribution Trt 1 -1 Trt*VisitWk  
  0 0 0 1 0 0 0 -1 / cl;  
  estimate "Trt diff at Week 16" GCABL 75th_of_BL_GCA_distribution Trt 1 -1 Trt*VisitWk  
  1 0 0 0 -1 0 0 0 / cl;  
  estimate "Trt diff at Week 28" GCABL 75th_of_BL_GCA_distribution Trt 1 -1 Trt*VisitWk  
  0 1 0 0 0 -1 0 0 / cl;  
  estimate "Trt diff at Week 40" GCABL 75th_of_BL_GCA_distribution Trt 1 -1 Trt*VisitWk  
  0 0 1 0 0 0 -1 0 / cl;  
  estimate "Trt diff at Week 52" GCABL 75th_of_BL_GCA_distribution Trt 1 -1 Trt*VisitWk  
  0 0 0 1 0 0 0 -1 / cl;  
  lsmeans "Trt lsmeans at Q1" trt01pn*avisitn / at blgcass=Q1 / cl;  
  lsmeans "Trt lsmeans at Q2" trt01pn*avisitn / at blgcass=Q2 / cl;  
  lsmeans "Trt lsmeans at Q3" trt01pn*avisitn / at blgcass=Q3 / cl;  
run;  
Repeat for change from baseline in ABC score
```

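### SAP 6.7.4 and its sample code 9.2.11 specify different models for the treatment effect at baseline GCA quartiles; under the text, the quartile effects average over a GCA class that cannot occur at that score

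*SAP*

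**What the plan says.** The primary GCA model in SAP 6.7.1 includes "treatment by baseline GCA classification factor interaction, treatment by baseline age group interaction", the interaction of GCA class with age group, and baseline GCA as a continuous covariate. The code in 9.2.1 matches: "model GCAchgBL = GCAclass Trt VisitWk Trt*Visitwk GCABL Agegroup Trt*GCAclass". The class interaction has no visit term there, so it is one constant across the four visits.

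For the exploratory question of whether the effect depends on baseline severity, SAP 6.7.4 says "the primary and key secondary MMRM models will be refit including the continuous baseline covariate by treatment interaction term" and adds the three-way term with visit. It names no term to be removed. P-values for the interaction terms, and least squares means "by treatment and visit at quartiles of GCA at baseline (25th, 50th and 75th percentiles) will be presented", are the planned output. A convergence sentence follows: "If this model fails to converge, the treatment by baseline age group interaction will be removed from the model".

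The code cited for this analysis, SAP 9.2.11, begins "model GCAchgBL = Trt VisitWk GCABL Trt*Visitwk Trt* GCABL Trt*Visitwk*GCABL" and ends "GCAclass Agegroup Genotype/ ddfm=kr solution". GCA class, age group and genotype are main effects only. Treatment by GCA class, treatment by age group and GCA class by age group are all absent. The note at the head of 9.2 says that dataset and variable names may differ from the real ones; it does not say that model terms may. SAP 7.2 records only that interaction terms were added to the MMRM, which does not settle the matter.

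The refit sentence also stands in Protocol 10.5.4, where it caused no conflict, because the primary model in Protocol 10.5.1 had GCA class as a main effect only.

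**The concern.** One planned analysis has two models, and for the GCA endpoint they answer different questions. With treatment by class and treatment by continuous score both in the model, the continuous interaction describes only how the effect changes within a class, after a common step at 70 has been taken out. The LSMEANS statements in 9.2.11 fix baseline GCA at the quartile but leave GCA class free and request no observed-margin weighting, so each class gets weight one half. A boy at a baseline of about 63 is given half of the effect belonging to >70, and a boy at about 77 half of the effect belonging to ≤70.

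The table exists to show whether benefit depends on baseline severity. Under the text it can leave out exactly the part of that dependence that occurs at 70, and its interaction p-value means something different from the code's. If this is not settled before unblinding, the choice can be made after the results are known.

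**Working it through.** **Planning figure reproduced.** SAP 4.2 states 80% power for 48 patients (32:16), difference 11, SD 11.6, two-sided 5%, up to 10% missing. A noncentral t calculation gives 80.7% with 28 and 14 evaluable, and 81.8% with 28.8 and 14.4. The inputs are therefore usable.

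**Algebra.** Write the Week 52 treatment effect at baseline x as τ + γx + d(class), with class terms d_low and d_high.

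- Text model, as LSMEANS evaluates it: τ + γx + (d_low + d_high)/2.
- Text model, evaluated in the class that x belongs to: τ + γx + d_low or d_high.
- Code model: τ + γx.

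Under the text, Q3 minus Q1 is γ(Q3 − Q1); the step d_high − d_low drops out. For a pure step of 5.5 versus 16.5 that is constant over visits, γ = 0 and every quartile shows (5.5 + 16.5)/2 = 11.0. The code model has no class interaction and expresses the step as a slope, which stays visible.

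**Numerical check in the four-visit model.** From the documents: 48 patients, 32:16, and SD 11.6 (SAP 4.2). Baseline GCA is normal with mean 70 and SD 15, restricted to 55–85; visit SDs are 3, 5, 8, 10, scaled by 1.16 so that Week 52 is 11.6; the correlation is AR(1) with 0.80 (SAP 9.3.2). The baseline quartiles are then 63.4, 70.0 and 76.6. The method is generalised least squares with known covariance and complete data. Age group and genotype are left out. The effect shapes are assumptions; the growing profile follows the differences 2, 5, 8, 11 in SAP 9.3.2.

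| Assumed effect | Text, Q1/median/Q3 at Week 52 | Code, Q1/median/Q3 at Week 52 |
|---|---|---|
| Step 5.5 vs 16.5, constant over visits | 11.0 / 11.0 / 11.0 | 7.1 / 11.0 / 14.9 |
| Same step at Week 52, growing over visits | 7.4 / 11.0 / 14.6 | 7.1 / 11.0 / 14.9 |
| Linear, 0.5 points per GCA point | 7.7 / 11.0 / 14.3 | 7.7 / 11.0 / 14.3 |

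These are averages over samples of 48. The large-sample limits differ by about 0.1: 7.5/11.0/14.5 for the text with a growing step, and 7.2/11.0/14.8 for the code with either step.

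**Why the growing step survives.** Treatment by class is one constant over visits, while the continuous interaction is free at each visit. At Week 16 the growing step is only 11 × 2/11 = 2 points, so the constant term absorbs little. In the large-sample fit, the Q1 effect is 7.48 with equal class weights and 7.02 in its own class, so the fitted class step is 2 × (7.48 − 7.02) = 0.92 points. The rest goes into the three-way term.

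**Precision.** For Q3 minus Q1 the standard error is about 6.6 under the text and 5.9 under the code: (6.6/5.9)² = 1.25, about a quarter more variance. At Q1 or Q3 alone the excess is roughly 10 to 14%, depending on the baseline sample; with a uniform 55–85 baseline and 29:14 evaluable, (5.4/5.1)² = 1.12.

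**The case against.** The strongest case against runs as follows.

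1. Full flattening needs the whole 11-point step to be present at Week 16 and to stay constant. The SAP's own simulation plans a mean difference of only 2 points at that visit. This stands: under the planned time course the distortion is small.
2. Even a constant step is not lost. It moves to the treatment-by-class coefficient, which would appear among the fixed-effect tests. With effects of 6 and 16 points and 29:14 evaluable, that coefficient is 10.0 with standard error 4.5. SAP 6.7.4 also plans a GCA-class interaction model with visit, and separate models for ≤70 and >70. This stands too, but a flat quartile table beside a subgroup step would still puzzle a reader who did not know which model produced it.
3. The convergence sentence names treatment by age group only, and fits the GCA-subgroup model described just before it. It therefore does not prove that treatment by GCA class stays in the refit. Agreed; the point rests on the refit wording, which removes nothing.
4. The code already has the simpler form. True, but its ESTIMATE statements put a coefficient on GCABL and none on Trt*GCABL or Trt*Visitwk*GCABL, so they do not give the treatment difference at a quartile.

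A reader might infer that the text would generally hide a baseline dependence at a severe cost in precision. A Week-52-only analysis would behave that way: a step at 70 is fully flattened and the variance of the Q3-minus-Q1 contrast is about 3.9 times larger. The SAP specifies a four-visit model, where neither holds in general. Nor is the primary inference touched.

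**Conclusion.** The text and code disagree, and the text version evaluates the GCA quartile effects partly in a class that does not occur at that score. How much this matters depends on the shape of the dependence: complete flattening for a step at 70 that is constant over visits, slight attenuation for one that grows, and for a linear trend only a modest loss of precision. The sizes rest on the assumed shapes, complete data, a known covariance, quartiles on either side of 70, and a model without age group or genotype.

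The point is minor. It concerns an exploratory analysis of GCA. The primary, key secondary and Family 3 tests are unaffected. In the ABC refit the continuous covariate is baseline ABC, which does not determine GCA class, so the impossible-class argument does not apply there; the mismatch of terms between text and code does.

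**What to change.** In SAP 6.7.4, state that for the GCA refit treatment by continuous baseline GCA (with visit) replaces treatment by GCA class, as in 9.2.11. Alternatively, keep treatment by GCA class and evaluate each quartile in its own class. Then:

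- say whether treatment by age group and GCA class by age group stay, for both the GCA and ABC refits, and make the convergence sentence and 9.2.11 agree;
- add the Trt*GCABL and Trt*Visitwk*GCABL coefficients to the ESTIMATE statements, so that they return the treatment difference at each quartile.

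Under the first option, by-arm least squares means still average the GCA class main effect over both classes. This cancels in the treatment difference, so the difference is the quantity to read.

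The cost is a sentence or two and a few lines of code, with no new data. The downside is that the refit relies on a linear baseline-by-treatment trend; a step at 70 is covered by the separate GCA-class analyses. The change should be made before unblinding.
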